5.2.1. Primary Objectives

- Compare plasma TFV concentrations measured by the aptasensor with those values quantitated by LC-MS/MS to determine agreement between the two methodologies, sensitivity, specificity, NPV, and PPV
- Determine if the TFV aptasensor can detect differences in the plasma TFV concentrations between high and low adherence dosing regimens and compare the mean difference to the difference calculated from values generated by LC-MS/MS

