6. INVESTIGATIONAL PLAN

6.1. Overall Study Design

This pilot, prospective, randomized study will screen approximately 20 healthy, non-pregnant, HIV negative, premenopausal women (aged 18-50) at EVMS who are not at risk of pregnancy and are at low risk for sexually transmitted infections (STIs) in order to have approximately 14 women complete all study visits. This study will examine the plasma, urine, and vaginal fluid from women in two dosing regimens of oral tablets: TDF/FTC (300/200 mg), 7 pills per week and TDF/FTC (300/200mg), 3 pills per week. Participants will be randomized to regimen as per the following schemata:

Table 3: Randomization Assignments

Regimen	N	Dose
Low Adherence (LA) Regimen	7	TDF/FTC (300/2200 mg), 3 pills/week, for a total of 6 ingested pills
High Adherence (HA) RRegimen	7	TDF/FTC (300/200 mg), 7 pills/week, for a total of 14 ingested pills

Participants will undergo the low adherence (LA) regimen or a high adherence (HA) regimen for two weeks, consisting of 5 visits.

Visit 1: At screening/enrollment, volunteers will be consented and undergo procedures to confirm they are eligible to continue in the study. Eligible participants will proceed to Visit 2.

Visit 2: Baseline blood, urine, and vaginal fluid will be collected. Participants will be randomized to dosing regimen and the first dose of TDF/TFC will be ingested in the clinic under direct observation. Participants will be instructed to take subsequent doses at home.

Dosing Contact: Participants will be sent reminder text messages to facilitate dosing occurring at the same time of day. Participants will text message the study coordinator to confirm ingestion of tablet. If the participant does not respond to a text within approximately 4 – 6 hours after it is sent, a reminder text will be sent.

Visits 3-5: Participants will return at 24 hours, 7 days, and 14 days after visit 2 for the pre-dose (for visits 3 and 4) collection of blood, urine, and vaginal samples.

Follow Up Contact: A final follow up site contact will be conducted approximately 1 – 2 weeks after the last visit to ask the participant about adverse events and concomitant medications. The participant will be exited unless there are symptoms that require follow up.

Table 4: Schedule of Evaluations

Single Dose Phase (EVMS only)				
	Visit 1 Screening	Visit 2 Baseline	Visit 3-5 24h, 7 days, and 14 days after Visit 2	Follow Up Contact
Informed consent	✓			
Review eligibility criteria, interval history	✓	✓		

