6.3. Number of Subjects

Approximately 20 women may be consented and undergo assessment procedures in order to have approximately 14 women who meet eligibility criteria complete the study. All 14 women will be randomly assigned to undergo either a low adherence dosing or high adherence dosing. All randomized participants will be included in the analysis.

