7.3.2. Target Enrollment

Participants who initiate product use but discontinue the study prior to completion may not re-enroll. Participants will be screened and enrolled so that approximately 14 women (7 per adherence cohort) complete all study visits.

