8.2. Visit 2: Baseline Pre-Dose Sample Collection

This visit will be scheduled for the early follicular phase of the menstrual cycle (for cycling women).

- An interval history will be collected.
- Eligibility criteria will be reviewed. If any lab tests reveal that the participant is not eligible, the visit should not proceed and the participant will not continue in the study.
- If indicated by signs or symptoms or history, a directed physical exam and/or urine pregnancy test will be performed. If pregnancy is diagnosed, the participant will be referred as necessary and will be discontinued.

- A vaginal swab for prostate specific antigen (PSA) will be obtained, if the PSA test indicates semen exposure, the visit will be re-scheduled.
- A urine sample will be obtained.
- Vaginal swabs will be obtained
- A blood sample (approximately 2 teaspoons) will be obtained.
- The participant will be randomized to the HA versus LA regimen and will take her first doses of TDF/FTC in the clinic under direct observation and the time of product ingestion will be recorded in the source document. The pill will be ingested after urine, vaginal and blood samples are obtained.
- The participant will confirm her contact information for the medication text reminder.
- Participants will be instructed to refrain from vaginal intercourse for 48 hours prior to visits 3 – 5.

8.3. Visits 3 – 5: 24 hours , 7 days, and 14 days after first dose

Visits 3, 4, and 5 will be scheduled for 24 hours, 7 days, and 14 days after initial dosing at Visit 2, respectively. The time of the visit will assure that it has been at least 24 hours since the participant's last dose of TDF/FTC. At each visit, the following procedures will be performed:

- The study staff will ask the participant if she followed the instructions from the previous visit, and ask about adverse events and concomitant medications.
- If indicated, a directed physical exam, pelvic exam and/or pregnancy test will be performed. If pregnancy is diagnosed, the participant will be referred as necessary and will be discontinued.
- Visits 4 and 5: Study staff will count the number of pills remaining and query the participant on compliance with her assigned dosing regimen.
- A vaginal swab for PSA will be obtained, if the PSA test indicates semen exposure, the participant will be reminded of the restrictions on vaginal intercourse, but the visit will proceed.
- A urine sample will be obtained.
- Vaginal swabs will be obtained

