9.4. Randomization and Blinding

This is a prospective, randomized trial. Participants and clinical study staff will not be blinded to the adherence dosing regimen. The laboratories and statistical/data analysts will be blinded to study treatment. Participants will be randomized 1:1 to the HA versus LA regimen, by simple randomization.

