14.3. Analysis Populations

The population includes healthy, non-pregnant, HIV negative women. The analysis population will include all participants who undergo baseline genital/rectal sampling.

The Full Analysis Set (FAS) will consist of all subjects who are randomized and have at least one post-baseline assessment. The FAS will be used to summarize study disposition, baseline characteristics, and all non-safety endpoints.

Evaluation of safety endpoints will be conducted using the Treated Population (TP), consisting of women with at least one dose of product use. If all subjects in the TP have at least one post-baseline assessment, then the TP will be identical to the FAS.

All populations will be defined based on the adherence regimen assigned (HA versus LA).

Additional populations or refinements to these definitions, if needed due to unanticipated circumstances, will be described in the SAP or statistical report.

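### Simple 1:1 randomization (9.4) will usually miss the 7 and 7 listed in Table 3; the cost is small, but the two should be reconciled.

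*Combined protocol and SAP*

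**What the plan says.** Section 9.4 gives the method: "Participants will be randomized 1:1 to the HA versus LA regimen, by simple randomization". It adds that "Participants and clinical study staff will not be blinded to the adherence dosing regimen".

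Section 6.1 introduces Table 3 with "Participants will be randomized to regimen as per the following schemata". The table, titled as randomization assignments, gives N = 7 for LA and N = 7 for HA without calling these expected counts. The synopsis carries the same table.

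Section 7.3.2 sets the completer target: "Participants will be screened and enrolled so that approximately 14 women (7 per adherence cohort) complete all study visits". Section 6.3 uses about 14 for women completing the study and also says "All 14 women will be randomly assigned to undergo either a low adherence dosing or high adherence dosing".

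Section 8.2 places assignment at Visit 2, after eligibility review and baseline sampling. Section 14.3 defines the main analysis set: "The Full Analysis Set (FAS) will consist of all subjects who are randomized and have at least one post-baseline assessment".

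One of the primary objectives in 5.2.1 is "Determine if the TFV aptasensor can detect differences in the plasma TFV concentrations between high and low adherence dosing regimens", although 14.4 describes the between-regimen comparison as the secondary analysis. For it, 14.4 plans an independent-samples t test, or Wilcoxon-Mann-Whitney if the data are not normal. It does not say whether the t test pools the variances. Section 14.1 bases the sample size on feasibility, and 14.4 treats p-values and intervals as descriptive.

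**The concern.** Under simple randomization each woman is assigned independently, so 7 per arm is only the expected count. Table 3 reads as a fixed allocation, and nothing in the protocol turns one into the other. There is no block size, no cap per regimen and no rule for assigning a replacement. The site cannot tell whether to stop at 14 whatever the split, to continue until each cohort has 7, or to direct late assignments. The last of these would no longer be simple randomization.

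What is at stake is the precision of the HA-LA difference and of the smaller cohort's summaries. If the SDs differ between regimens, the behaviour of a pooled-variance t test and its confidence interval is also affected.

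**Working it through.** **Inputs.** Simple 1:1 allocation (9.4); 14 women randomized (6.3); 7 and 7 (Table 3); about 20 consented (6.3). The documents give no SD, effect size, alpha or power. The only planned figure to reproduce is 7 + 7 = 14, which is consistent.

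**1. Distribution of the split.** The number assigned to HA is Binomial(14, 0.5), so P(7:7) = C(14,7)/2^14 = 3432/16384 = 20.9%.

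**2. Precision.** With equal SDs, the standard error relative to 7:7 is sqrt[(1/a + 1/b)/(2/7)]. For 10:4 this is sqrt[(0.100 + 0.250)/0.2857] = 1.107.

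| Split (either direction) | Probability | Increase in standard error |
|---|---|---|
| 7:7 | 20.9% | 0 |
| 8:6 | 36.7% | 1.0% |
| 9:5 | 24.4% | 4.3% |
| 10:4 | 12.2% | 10.7% |
| 11:3 | 4.4% | 21.9% |
| 12:2 | 1.1% | 42.9% |

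- 9:5 or better: 82.0%. 10:4 or worse: 18.0%. 11:3 or worse: 5.7%.
- 7:7 and 8:6 together make up 57.6%, so the median increase is the 8:6 value, 1.0%. The mean, leaving out the negligible 14:0 case, is 4.4%.

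**3. If more than 14 are randomized.** P(at least 7 in each arm) is 54.6% with 16 randomized, and 88.5% even if all 20 consented women were randomized. Continuing until both arms reach 7 would need 16.9 women on average.

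**4. Test size if the t test pools variances.** Simulated normal data, two-sided nominal 5%, with assumed HA:LA SD ratios:

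| Split | Test | Ratio 1 | Ratio 1.5 | Ratio 2 |
|---|---|---|---|---|
| 7:7 | pooled | 5.0% | 5.2% | 5.6% |
| 4 HA:10 LA | pooled | 5.0% | 9.7% | 14.0% |
| 10 HA:4 LA | pooled | 5.0% | 2.4% | 1.5% |
| 4 HA:10 LA | Welch | 5.5% | 5.9% | 6.0% |

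Averaged over the binomial splits, the pooled test's size is about 5.6% at ratio 1.5 and 6.5% at ratio 2, because liberal and conservative splits partly offset each other. The split 4 HA:10 LA has probability C(14,4)/2^14 = 1001/16384 = 6.1%. Splits still shorter of HA are worse; 4 or fewer HA has probability 1471/16384 = 9.0%. Welch stays between 4.7% and 6.0% at 7:7, 4:10 and 10:4 for all three ratios.

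**5. Predictability of a balanced list.** Enumerating all 3432 orderings of 7 HA and 7 LA and counting the run of equal assignments at the end: the last assignment is always deducible, at least two are in 46.2% of lists, and the mean is 1.75 of 14. Simple randomization has no deducible assignments.

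**The case against.** Simple randomization can be defended here. Clinical staff at a single site are unblinded, and it is the one scheme under which no assignment can be deduced. Its price is a median 1.0% in the standard error. The 14 in 6.1 and 7.3.2 is approximate, the 7 per cohort in 7.3.2 refers to completers, and no allocation scheme guarantees completers. Section 7.3.2 can also be read as enrolling towards that target, in which case the probabilities for a fixed 14 do not apply directly. All of this stands, and it is why keeping simple randomization is an acceptable option. It does not remove the mismatch, because Table 3 states its assignment counts without qualification and enrolling further would not ensure 7 per arm either.

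A reader might infer more than the documents support:

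- **That an uneven split biases the HA-LA comparison or weakens the main assay analysis.** It does neither. Allocation stays random. The aptasensor versus LC-MS/MS comparison, which 14.4 names as primary, pools all women, and the specificity samples are taken before dosing.
- **That the planned t test has a 14% error rate.** That figure needs 4 HA:10 LA, an SD ratio of 2 that the documents do not supply, and a pooled-variance test that 14.4 does not specify. If the data fail the normality check, the t test is not used at all. Section 14.4 also disclaims control of Type I error.

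**Conclusion.** The point holds as a minor one. The protocol lists arm sizes that its own method delivers about one time in five, and no section reconciles them. Precision loss is at most 4.3% in 82.0% of allocations, though a split of 11:3 or worse (5.7%) would cost 21.9% or more. The standard-error figures assume equal SDs and 14 randomized. The test-size figures assume normal data and illustrative SD ratios. Averaged over splits, a pooled test adds roughly 0.4 percentage points at ratio 1.5 (5.6% against 5.2% at 7:7) and 0.9 at ratio 2 (6.5% against 5.6%). For a descriptive pilot sized on feasibility, none of this threatens the conclusions. It merits a change because the change is cheap and a poor split cannot be repaired after enrolment.

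**What to change.** Choose one of two options in 9.4.

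1. **Balanced list.** Replace simple randomization with a concealed, pre-generated list balanced at 14, held by someone who does not enrol participants and opened only after eligibility is confirmed. It can be one random permutation of 7 HA and 7 LA, or permuted blocks of undisclosed sizes summing to 14 (for example 4, 4 and 6 in random order). Blocks of 4 alone give 7:7 at the 14th woman only two-thirds of the time. Section 8.2 already puts eligibility review before assignment, so only concealment and custody are new.
2. **Simple randomization kept** for its unpredictability. Relabel the 7 and 7 in Table 3, the synopsis table and 7.3.2 as expected numbers.

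In either case, specify the Welch t test in 14.4 and state how a replacement, if any, is assigned.

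**Cost.** One or two sentences in 9.4 or a relabelling, one word in 14.4 and, for option 1, a list made before first enrolment. Option 1 brings the predictability shown above. Opening after eligibility limits what staff can do with that knowledge but does not hide it, and a regimen-matched replacement is fully predictable. Balance at 14 randomized is also not balance in the FAS. A dropout after Visit 3 with a matched replacement gives 8:7 (standard error 3.2% below 7:7). A dropout with no post-baseline assessment and no replacement gives 7:6 (4.1% above).

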10. STUDY DRUG MATERIALS AND MANAGEMENT

10.1. Description of Study Drug

10.1.1. Emtricitabine/tenofovir disoproxil fumarate (F/TDF)

The F/TDF tablet is marketed as Truvada®. Each tablet contains 200 mg of emtricitabine and 300 mg of tenofovir disoproxil fumarate (which is equivalent to 245 mg of tenofovir disoproxil). The tablets are blue, capsule-shaped, film-coated with a length of 19 mm and a width of 8.5 mm, and are debossed with “GILEAD” on one side and with “701” on the other side. Excipients include: [Tablet Core] croscarmellose sodium, lactose monohydrate, magnesium stearate, microcrystalline cellulose, and [Film Coating] polyvinyl alcohol, titanium dioxide, polyethylene glycol, talc, and iron oxide black. Thirty (30) tablets are packaged in 75 ml, white, high density polyethylene bottles with a three-gram desiccant canister (without patent number) present in each bottle. Each bottle is enclosed with a white, continuous thread, child-resistant polypropylene screw cap with an induction-sealed, aluminum-faced liner. Participants will receive enough study drug at visits 3 and 4 to take them to their next follow up appointment. Study drug will be dispensed in accordance with the Clinical Research Center standard operating procedure.

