As such, there is an opportunity to evaluate a new method of measuring adherence in a reliable, objective, and cost-effective manner. Aptamers are DNA- or RNA-based ligands capable of binding practically any molecular target with high specificity, including small molecules such as antiretroviral drugs⁸. Aptamers have advantages over antibodies. They are more stable and made through a process that is more economical and reproducible, which increases the aptamer's potential capability of being more specific than its antibody counterpart. Therefore, aptamers are being used as capture molecules for biosensor platforms, which are becoming smaller than previous models, more portable, more sensitive and quantitative (rivaling LC-MS/MS), require less sample volume, and simpler to use. Therefore, aptamer-based biosensors or "aptasensors," have great potential for real-time therapeutic drug monitoring. We will be utilizing a previously validated DNA aptamer specific for TFV and applying it to a biosensor platform.

This study will focus on determining the sensitivity and specificity of the TFV aptasensor and assess its ability to distinguish TFV levels associated with low and high adherence using biological fluids collected from women taking TDF/FTC at different dosing regimens.

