6.4. Treatment Assignment

Women will be randomized to one of two in two dosing regimens of oral tablets: TDF/FTC (300/200 mg), 7 pills per week and TDF/FTC (300/200mg), 3 pills per week.

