7.2. Exclusion Criteria

Volunteers must not meet any of the following criteria prior to baseline sampling:

1. Currently pregnant
2. Currently breastfeeding or planning to breastfeed during the course of the study
3. In the last three months, diagnosed with or treated for any STI

4. Positive test for HIV, or Hepatitis B surface antigen (HBsAg)
5. Systemic use in the last two weeks or anticipated use during the study of any of the following: antiretrovirals (e.g. Viread®, Atripla®, Emtriva®, or Complera®), or drugs that may interact with TFV (e.g., protease inhibitors, anticonvulsants, antimycobacterials, St. John's Wort).
6. Participation in any other investigational trial with use of a drug/device within the last 30 days or planned participation in any other investigational trial with use of a drug/device during the study
7. Grade 2 or higher laboratory abnormality, per the 2014 update of the Division of AIDS, National Institute of Allergy and Infectious Disease (DAIDS) Table for Grading the Severity of Adverse Events, or clinically significant laboratory abnormality as determined by the clinician
8. Abnormal finding on laboratory or physical examination or a social or medical condition in the volunteer which, in the opinion of the investigator, would make participation in the study unsafe or would complicate interpretation of data

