14.4. Statistical Analysis

Sample size is based on feasibility rather than statistical considerations; thus, analysis will be primarily descriptive. Participant flowchart (e.g. number screened, number with sampling) will be provided. All populations will be defined based on the adherence regimen.

Evaluation of Study Objectives: Study objectives will be evaluated by clinical review of descriptive summaries and graphical displays.

Primary analysis of this study will evaluate the performance of the TFV aptasensor by comparing its measurements of the concentrations of TFV in clinical samples from all women with those values obtained from LC-MS/MS. Correlation and agreement between the TFV levels measured by the aptasensor and LC-MS/MS will be analyzed using scatterplot and linear regression. Continuous variables will be compared between values measured with the aptasensor versus LC-MS/MS using paired comparisons. From this comparison, sensitivity, specificity, NPV, and PPV of the aptasensor will also be determined. Confidence intervals will be calculated to assess precision and margin of error of those

measures. Using the 14 baseline pre-dose samples, each woman will be her own control, and these pre-dose samples will be used for the assessment of specificity and NPV.

The secondary analysis of this study will evaluate whether the aptasensor can detect differences in TFV levels between the two independent cohorts of women taking TDF/FTC at different dosing regimens representing high (7 pills/week) and low adherence (3 pills/week). We will compare the two independent cohorts using an independent samples t test for normally distributed data or a Wilcoxon-Mann-Whitney test for non-parametric data. TFV concentrations from the LA and HA cohorts will be characterized using descriptive statistics (mean, median, interquartile range, minimum and maximum). The values will be compared between the high adherence and low adherence groups as well as comparing the mean difference between groups generated by the aptasensor to that difference generated by LC-MS/ MS. Distributions will be checked to determine normality so as to determine the appropriate statistical test.

Descriptive Statistics: Categorical variables will be summarized by frequencies and percentages. Continuous variables will be summarized by means, standard deviations, medians, quartiles, minima and maxima.

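### The planned accuracy figures can show that the sensor separates dosed from undosed samples, but not that it responds to tenofovir rather than emtricitabine

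*Combined protocol and SAP*

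**What the plan says.** Section 4 sets the aim: "This study will focus on determining the sensitivity and specificity of the TFV aptasensor". Section 5.1 repeats it as the purpose of the trial.

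There is one study product. Section 10.1.1 states: "Each tablet contains 200 mg of emtricitabine and 300 mg of tenofovir disoproxil fumarate". Section 6.4 assigns two regimens of that tablet, seven or three pills a week. No arm receives either drug alone.

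Section 14.4 compares the sensor with LC-MS/MS TFV by scatterplot, linear regression and paired comparisons, and adds: "From this comparison, sensitivity, specificity, NPV, and PPV of the aptasensor will also be determined". For the 14 baseline specimens it says that "these pre-dose samples will be used for the assessment of specificity and NPV". The exclusion criteria in Section 7.2 keep those specimens free of both drugs, since they bar "Systemic use in the last two weeks or anticipated use during the study of any of the following: antiretrovirals", and an FTC product is among the examples.

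On selectivity, Section 4 offers one sentence: "We will be utilizing a previously validated DNA aptamer specific for TFV and applying it to a biosensor platform". The protocol describes no FTC measurement, no sample containing FTC without TFV, no interference test and no cut-off for a positive reading.

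**The concern.** Specificity is only as informative as the negatives it is computed on. Here every negative lacks both drugs, and every dosed sample comes from a woman who took both. A two-by-two table built on these samples contrasts dosed with undosed. It has no cell in which FTC is present and TFV absent, so it cannot say which of the two drugs the sensor reads. The contrast between high adherence (HA) and low adherence (LA) carries the same confounding, because more TFV pills are also more FTC pills.

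What is at stake is how the result is read. The stated aim is the specificity of a TFV sensor, and the synopsis says the statistics will guide its further development. A high specificity from this trial would support the statement that the sensor is quiet in drug-free fluid. It would not support the statement that the sensor is selective for TFV.

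**Working it through.** **Inputs from the protocol**
- Women: 14, seven per cohort (Section 7.3.2).
- Sampling: one pre-dose visit and three post-dose visits at 24 hours, 7 days and 14 days (Sections 8.2 and 8.3).
- LA example schedule (Table 7): doses on study days 1, 3, 5, 8, 10 and 12; visits on days 2, 8 and 15.
- The protocol gives no FTC concentrations, detection limit, variances or cut-off. Values for these below are assumptions.

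**Step 1: the protocol's own count.** 14 women × 1 baseline = 14 negatives, which reproduces the 14 in Section 14.4. Post-dose samples: 14 × 3 = 42. Total per fluid (plasma, the primary fluid, and likewise urine): 14 + 42 = 56. FTC and TFV exposure coincide in all 56.

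**Step 2: score a hypothetical sensor that reads FTC only and is silent without it.** Specificity on the pre-dose samples is 14/14 = 100%, exact (Clopper-Pearson) 95% CI 76.8% to 100%. This needs only that the pre-dose samples contain no FTC.

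**Step 3: its sensitivity.** In the LA example schedule, visit 4 falls (8 − 5) × 24 = 72 hours after the last dose, and visit 5 falls (15 − 12) × 24 = 72 hours after. That is 7 women × 2 visits = 14 of the 42 dosed samples. The HA samples, and the LA samples at visit 3, are at about 24 hours. Assume all 42 are positive by LC-MS/MS, and vary the number of 72-hour samples in which FTC is undetectable:

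| FTC undetectable at 72 h | Sensitivity (exact 95% CI) | NPV |
|---|---|---|
| 0 of 14 | 42/42 = 100% (91.6–100) | 14/14 = 100% |
| 7 of 14 | 35/42 = 83.3% (68.6–93.0) | 14/21 = 66.7% |
| 14 of 14 | 28/42 = 66.7% (50.5–80.4) | 14/28 = 50% |

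Section 9.4 specifies simple randomization, so the 7:7 split is not fixed. With 4 to 10 women in LA, 8 to 20 samples would fall at 72 hours.

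**Step 4: would agreement with LC-MS/MS expose it?** Assume lognormal TFV and FTC in dosed samples, each with CV 50%, so σ² = ln(1 + 0.25) = 0.223, with log-scale correlation ρ between the drugs. For dosed samples, r = (exp(ρσ²) − 1)/(exp(σ²) − 1). This gives 0.277, 0.676 and 0.890 for ρ = 0.3, 0.7 and 0.9; simulation of 42 samples gives means of 0.28, 0.68 and 0.89.

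Now add the 14 pairs of zeros. They are a fraction 14/56 = 0.25 of the data, and CV² is also 0.25, so the large-sample pooled value is (0.25 r + 0.25)/(0.25 + 0.25) = (1 + r)/2 = 0.64, 0.84 and 0.94. Simulation of 56 samples gives means of 0.65, 0.85 and 0.95.

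| ρ (assumed) | r, 42 dosed samples | r, all 56 samples |
|---|---|---|
| 0.3 | 0.28 | 0.65 |
| 0.7 | 0.68 | 0.85 |
| 0.9 | 0.89 | 0.95 |

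A second simulation built in the 72-hour LA samples (assumed TFV half-life 17 hours, FTC half-life 0.5 to 1.0 times that, log-SD 0.4, correlation 0.7, sensor calibrated at 24 hours). The FTC:TFV ratio at 72 hours then ranged from unchanged to 0.14 of its 24-hour value. Pooled over 56 samples, an FTC-only sensor still gave r of about 0.92 and a slope of 0.92 to 0.97.

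**The case against.** Four points on the other side deserve weight.

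*The reference is measured TFV, not dosing status.* Section 14.4 plans a scatterplot, regression, paired comparisons and a check of the sensor's HA–LA difference against the LC-MS/MS difference. A reader might infer that cross-reaction could show there only as a slope or mean bias, indistinguishable from calibration error. That holds only if the FTC:TFV ratio is constant. If it varies between women, or between 24 and 72 hours, the error also appears as scatter and as bias that depends on regimen and visit. Under the Step 4 assumptions, even after perfect mean calibration, the 95% limits of agreement, exp(±1.96 σ√(2(1 − ρ))), span a factor of about 3.0, 2.0 or 1.5 either way. An FTC-only sensor would look poor among dosed samples in the first two cases. This part of the objection stands. What remains is that pooling with the zeros hides much of the signal, and that partial cross-reaction at a near-constant ratio could pass unnoticed.

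*Prior validation exists.* Section 4 states that the aptamer is validated and TFV-specific, and Section 5.2.2 refers to preclinical work on the sensor's limit of detection. A clinical protocol need not reproduce bench data. But no interferent is named, and nothing is given on FTC for the assembled sensor. Existing data, if cited, would largely answer the point.

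*Specificity here is diagnostic, not chemical.* Section 14.4 does disclose that it comes from pre-dose samples. That is why the remedy is mainly one of labelling.

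*This is a descriptive pilot sized for feasibility.* That is true, and it keeps the point minor.

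**Conclusion.** The point holds in a limited form. TFV and FTC exposure are completely confounded by design, so the two-by-two measures cannot by themselves establish selectivity for TFV. The 14/14 specificity of an FTC-only sensor follows directly from the choice of negatives.

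Three stronger readings are not supported:
- A reader might infer that an FTC-only sensor must score 100% on everything. The documents show that every dosed woman took FTC, not that FTC is detectable in every dosed sample. Sensitivity could be as low as 66.7% if FTC has gone from the 14 LA samples at about 72 hours. With no stated cut-off, 72-hour samples that are TFV-negative by LC-MS/MS but FTC-positive would also become false positives and lower PPV.
- A reader might infer that the sensor does cross-react. Nothing in the documents says so, and any figure for over-reading would rest on a cross-reactivity and an FTC:TFV ratio that they do not give.
- A reader might infer that the LC-MS/MS comparison is useless here. It is an indirect check, weakened by pooling.

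The sensitivity range rests on the example schedule, a 7:7 split and all 42 dosed samples being LC-MS/MS-positive. The correlations rest on the assumed CV of 50% and the assumed ρ. This is a low-severity improvement to labelling and reporting.

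**What to change.** 1. In Sections 5.1 and 14.4, state that specificity is estimated in drug-free fluid and does not test the sensor's response to TFV against FTC.
2. In Section 14.4, report correlation and regression among post-dose samples separately from pre-dose samples, so that the shared zeros do not inflate agreement.
3. Add one table of the sensor-minus-LC-MS/MS difference by regimen and visit. Bias that changes between the 24-hour and 72-hour samples would show here.

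These need no new samples, visits or assays. The cost is wording, one table and a narrower claim.

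Optionally, cite any existing FTC cross-reactivity data for the assembled sensor. If the sponsor chooses to read drug-free aliquots with FTC added, those readings belong in a separate analytical table and should not be counted among the clinical reference-negatives, because that would change the planned 14-sample specificity. Spiking would be a new bench procedure, and the protocol gives neither a leftover aliquot volume nor a spiking level.
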